13.4 Primary Objective, Endpoint(s), Analysis Plan

The primary endpoint of this randomized trial is to compare the absolute change in IL-1 β cytokine levels (measured by Luminex assay) in the gastric mucosa from baseline to 6 months among participants randomly assigned to receive either Meriva® or placebo. Statistical considerations regarding sample size and study power are based on this primary study endpoint.

In total, approximately 100 individuals will be screened and 50 participants will be randomized to receive Meriva® (n=25) or placebo (n=25), in order to achieve complete trial data on 22 evaluable participants in each arm (44 evaluable total). This assumes a 10% over accrual buffer after randomization to account for participants who are deemed ineligible, cancel, or dropout for other reasons during the intervention period. We expect to randomize approximately 5-6 participants per month across both the Puerto Rico and Honduras recruiting sites.

The null hypothesis for this study is that the absolute change in the IL-1 β values from baseline to 6 months is the same or increased for Meriva® vs. placebo. The alternative hypothesis is that Meriva® intervention will lead to a significant decrease in IL-1 β cytokine levels from baseline to 6 months, as compared to placebo. The proposed sample size and power calculations are based on prior unpublished data, where IL-1 β levels are expected to have a mean of approximately 14 pg/mg protein at baseline, with a standard deviation of about 7.5 pg/mg of protein. This prior mouse study showed a 2-fold decrease in IL-1 β levels for curcumin-treated mice (from around 14 to 7 pg/mg protein, comparing the vehicle [equivalent to placebo] treated to curcumin-treated mice). Based on this prior data, we expect the Meriva®-treated participants to have a mean decrease of about 7 pg/mg of protein or more by 6 months after baseline, leading to a 6 month IL-1 β mean of 7 pg/mg of protein in the Meriva®-treated participants (2-fold decrease). For the placebo group, we expect the mean IL-1 β to either stay the same or decrease slightly from baseline to 6 months.

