With 22 evaluable participants per arm, this study yields 88% power to detect a mean decrease of 7 pg/mg protein or more in IL-1 β level in the Meriva® intervention arm compared to a mean decrease of 0.5 pg/mg protein in the placebo arm (from baseline to 6 months), with an overall 1-sided significance level of 0.05 (2 sample t-test, assuming the same standard deviation of 7.5 pg/mg protein in each arm). If the data are not normally distributed, we will use the Wilcoxon Rank-Sum test for the primary endpoint analysis.

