13.6 Reporting and Exclusions

All randomized participants who are evaluated at baseline and 6 months and have IL-1 β cytokine levels from those time points will be evaluable for the primary endpoint of this study using the modified intent-to-treat principle. We plan to over-randomize assuming 12% drop out within 6 months to ensure an adequate sample size in the primary analysis cohort. There will be

no imputation for missing data. A summary and listing of all major protocol violations will be provided. All details will be given in the final study report and/or manuscript. Participants lost to follow-up will be censored on the last date of assessment (or contact) and as appropriate for analyses that are dependent upon length of study participation.

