13.8 Evaluation of Response

All randomized participants who are evaluated at baseline and 6 months and have IL-1 β cytokine levels from those timepoints will be evaluable for the primary endpoint of this study using the modified intent-to-treat principle. All conclusions regarding efficacy will be based on all participants who completed both baseline and 6 months and have IL-1 β cytokine levels from those timepoints as well. Subanalyses may be performed on the subsets of participants, excluding those for whom major protocol deviations have been identified (e.g., early death due to other reasons, early discontinuation of intervention, major protocol violations, etc.). However, sub-analyses may not serve as the basis for drawing conclusions concerning efficacy, and the reasons for excluding participants from the analysis should be clearly reported. For all measurements of response (i.e. the primary endpoint), the 95% confidence intervals will also be provided.

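### The 88% power for change in IL-1β uses an SD documented only for the baseline level; no SD of change or within-person correlation is given, and the planned test leaves the baseline value unused as a covariate

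*Combined protocol and SAP*

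**What the plan says.** Sections 8.1 and 13.4 define the primary endpoint as the absolute change in gastric mucosal IL-1β from baseline to 6 months, compared between arms. Section 13.4 adds: "Statistical considerations regarding sample size and study power are based on this primary study endpoint".

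On the inputs, Section 13.4 says: "The proposed sample size and power calculations are based on prior unpublished data". It expects IL-1β to have a "mean of approximately 14 pg/mg protein at baseline, with a standard deviation of about 7.5 pg/mg of protein". The only description of the prior result is a fall from about 14 to 7 pg/mg protein, "comparing the vehicle [equivalent to placebo] treated to curcumin-treated mice".

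The power statement is 88% with 22 evaluable participants per arm, for mean decreases of 7 (Meriva) and 0.5 (placebo), at one-sided 0.05: "2 sample t-test, assuming the same standard deviation of 7.5 pg/mg protein in each arm". The fallback is: "If the data are not normally distributed, we will use the Wilcoxon Rank-Sum test for the primary endpoint analysis".

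Two other provisions matter. Section 13.6 counts as evaluable those who were assessed at baseline and 6 months and whose "cytokine levels from those time points will be evaluable for the primary endpoint of this study". Section 13.8 says that for the primary endpoint "the 95% confidence intervals will also be provided".

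**The concern.** The t-test is applied to changes, so the SD it needs is the SD of the change. The only documented 7.5 is the SD of a level at one visit. The two coincide only under a particular correlation between a person's two measurements, and the plan does not mention one.

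The prior data, as described, do not fill the gap. A comparison of vehicle-treated with curcumin-treated mice is between groups. The mouse work in Section 2.3 measured its endpoints once, at sacrifice, so it could not yield an SD of change. Section 13.4 does not say whether this is the same experiment.

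The 88% is the stated justification for 22 evaluable participants per arm. If the SD of change is larger than 7.5, a null result would be weaker evidence than the plan implies.

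**Working it through.** **Inputs from Section 13.4.** n = 22 per arm; difference in mean change = 7 − 0.5 = 6.5; SD = 7.5; one-sided alpha = 0.05.

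**Step 1: reproduce the 88%.** Noncentrality = 6.5 / (7.5 × √(2/22)) = 2.874, with 42 degrees of freedom and critical t = 1.682. Power from the noncentral t is 88.2%, so the plan's figure reproduces.

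This does not show what kind of SD the 7.5 is. A t-test of 6-month levels, with means of 7 and 13.5 (14 minus the two decreases) and SD 7.5, has the same difference of 6.5 and therefore the same 88.2%.

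**Step 2: limits on the SD of change, with no assumption about rho.** Solving the same formula, 88% needs an SD of change of at most 7.52, and 80% needs at most 8.53.

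**Step 3: from SD of level to SD of change.** With SDs s0 at baseline and s6 at 6 months,

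SD of change = √(s0² + s6² − 2·rho·s0·s6).

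If s0 = s6 = 7.5, this is 7.5 × √(2(1 − rho)), which equals 7.5 only at rho = 0.5. Neither rho nor s6 is in the documents, so the cases below are assumptions, with s0 = 7.5 and the same s6 in both arms.

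**Step 4: the ANCOVA alternative.** Regressing the 6-month value on arm and baseline leaves a residual SD of s6 × √(1 − rho²). At equal SDs of 7.5 this is never above 7.5. ANCOVA power was obtained by simulation with normal data and 200,000 trials per cell. Baseline was drawn at random in each trial, so chance imbalance is included.

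| 6-month SD | rho | SD of change | Power, change-score t-test | Power, ANCOVA |
|---|---|---|---|---|
| 7.5 | 0 | 10.61 | 63.9% | 87.5% |
| 7.5 | 0.3 | 8.87 | 77.2% | 90.1% |
| 7.5 | 0.5 | 7.50 | 88.2% | 94.3% |
| 7.5 | 0.7 | 5.81 | 97.8% | 98.9% |
| 9 | 0 | 11.72 | 56.6% | 75.3% |
| 9 | 0.3 | 9.84 | 69.5% | 78.7% |
| 9 | 0.5 | 8.35 | 81.4% | 85.1% |
| 9 | 0.7 | 6.54 | 94.5% | 94.7% |

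A separate simulation of 60,000 trials per cell agreed with every ANCOVA figure to within 0.3 points.

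Two further assumed cases for the change-score test, at rho 0, 0.3, 0.5 and 0.7:
- Favourable: the 6-month SD halves to 3.75 in the Meriva arm only. Power is about 72, 83, 92 and 98%.
- Unfavourable: SD 10 at both visits in both arms. Power is about 44, 56, 68 and 86%.

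**Step 5: the rank fallback.** This was simulated with normal data and 100,000 trials per cell. With 6-month SD 7.5, the Wilcoxon test on change against a baseline-adjusted rank test gives 61.5 against 86.0% at rho 0, and 97.1 against 98.0% at rho 0.7. With 6-month SD 9 and rho 0.7 the order reverses: 93.3 against 92.2%. Type I error in the fallback simulations was 4.8 to 5.1% for the Wilcoxon test, ANCOVA and the adjusted rank test.

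**The case against.** The best defence is that nothing here is shown to be wrong. Section 13.4 presents 7.5 openly as an assumption, the arithmetic follows from it, and the unpublished data behind it cannot be inspected. With SD 7.5 at both visits, 88% is conservative for any rho above 0.5. All of that stands.

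A reader might infer that the trial is underpowered, or that the SD of a level was entered by mistake. The documents support neither reading. The power statement does not label its 7.5 as an SD of level or of change, and the 88% fits both. For the same reason, the sponsor should be asked what the figure is and where it comes from, rather than told that it is a single-visit SD.

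A reader might also infer that the change-score t-test is invalid. It is valid. The case for ANCOVA is efficiency: its power depends less on the unknown rho. It does not remove dependence on the SD: at rho 0, its power falls from about 87% to 75% when the 6-month SD is 9 instead of 7.5.

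One further objection limits the remedy. A baseline-adjusted rank test gives no estimate or interval in pg/mg protein, whereas the rank-sum test on change has a matching Hodges-Lehmann shift interval. Because Section 13.8 requires 95% confidence intervals, the adjusted rank test cannot simply replace the fallback.

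Finally, rewording the power statement alone changes neither the sample size nor the analysis. The practical gain lies in the choice of test.

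**Conclusion.** The point holds as a gap in support for a key input, together with an avoidable loss of efficiency. The 88% is correct if the SD of change is 7.5. The plan gives no ground for that value, and the direction of any error is unknown.

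At 22 per arm, power is at least 80% only if the SD of change is at most about 8.5; this needs no assumption about rho. The 64 to 98% range for the change-score test rests on assumed rho from 0 to 0.7 with SD 7.5 at both visits. A 6-month SD of 9 gives 57 to 94.5%.

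Under the same two sets of assumptions ANCOVA gives about 87 to 99% and 75 to 95%. The gain is large at low rho and about one point or less at rho 0.7. The confidence interval required by Section 13.8 will show the precision achieved, but it does not supply the missing design input.

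**What to change.** 1. **Primary test.** Before unblinding, amend Section 13.4 so that the primary test is an ANCOVA of 6-month IL-1β on arm and baseline IL-1β. Report the adjusted difference in pg/mg protein with its 95% confidence interval. Using the change as the outcome, with the same covariates, gives the same arm effect, so the comparison of changes is kept. Section 13.6 already requires a baseline value for every evaluable participant, so no further participants, biopsies or assays are needed. The powers above are for arm and baseline alone; adding the stratification factors is a separate choice.

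2. **Power statement.** In Section 13.4, state the SD of change, or rho and the SD at each visit, with the source. If no source exists, present 88% as conditional on an SD of change of 7.5, and show power over a range that varies both rho and the SD.

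3. **Fallback.** If a rank-based fallback is kept for non-normal data, use a baseline-adjusted rank test for the p-value only if an interval in pg/mg protein is also specified, to meet Section 13.8. It is not better in every case (about 92 against 93% in one case above).

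**Cost.** Item 2 is a text change. Items 1 and 3 are a protocol amendment in a trial already accruing, and under Section 14.3 need DCP and CIRB/REB approval before implementation. The stated power becomes conditional, and looks less favourable for the change-score test at low rho.

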10.2.2 Research Blood Specimens

Blood specimens for endpoint analyses as well as optional blood specimens for future unspecified research will be drawn at Baseline, Month 3, and Month 6/Post-intervention. Blood specimens will be processed into serum, plasma, and buffy coat, and shipped to BAP overnight. See Section 10.1 for address. Detailed instructions for collecting, processing, labeling, and shipping the specimens can be found in the instructions provided in each blood specimen kit.

10.2.3 Tissue Specimen Collection and Submission for Central Pathology Review Histological confirmation of MAG, GIM, or both for eligibility will be determined based on local pathology review of the specimens collected during the baseline EGD procedure (See Appendix D). Representative specimens (blocks and/or slides) will be submitted for central review and confirmation. Digital images of all specimens will be created for the review and archiving processes. Discrepancies between local and central pathologists will be resolved on a case-bycase basis by teleconference or video conference between the local and central pathologists. Central pathology review will be performed at one time, when the study is completed, and is not part of the baseline evaluation.

Telepathology will be used to accomplish the goals of the study, and will be used as a pathology training platform. All specimens (histology slides) are de-identified. All study slides will be scanned and digitally archived for central review, discussion and training.

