13.2 Randomization/Stratification

Participants will be randomized in a 1:1 fashion to one of two arms (Meriva® vs. placebo), using a dynamic allocation procedure called the Pocock-Simon, which balances the marginal distributions of the stratifications factors across the intervention groups and has been shown to be able to accommodate a large number of factors (10-20) without difficulty. For this study we will use the following stratification factors (collected at baseline, prior to randomization): enrolling site (Honduras or Puerto Rico) and gastric mucosal histologic diagnosis (MAG, GIM, or both).

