13.3 Accrual and Feasibility

Planned Accrual Estimates

	DOMESTIC PLANNED ENROLLMENT REPORT Ethnic Categories					
Racial Categories	Not Hispanic or Latino		Hispanic or Latino			
	Female	Male	Female	Male	Total	
American Indian/Alaska Native	0	0	0	0	0	
Asian	0	0	0	0	0	
Native Hawaiian or Other Pacific Islander	0	0	0	0	0	
Black or African American	0	1	0	0	1	
White	1	0	5	16	22	
More Than One Race	0	0	1	1	2	
Total	1	1	6	17	25	

	INTERNATIONAL PLANNED ENROLLMENT REPORT Ethnic Categories					
1000 2000 000 100 ISS.						
Racial Categories	Not Hispanic or Latino		Hispanic or Latino		¥1. II	
	Female	Male	Female	Male	Total	
American Indian/Alaska Native	0	0	0	0	0	
Asian	0	0	0	0	0	
Native Hawaiian or Other Pacific Islander	0	0	0	0	0	
Black or African American	0	0	0	1	1	
White	1	0	5	16	22	
More Than One Race	0	0	1	1	2	
Total	1	0	6	18	25	

The study design requires a total of 100 participants for screening evaluation with approximately 50 moving forward to randomization (25 total participants per arm) due to anticipated screen failures of up to 50% prior to randomization. We further expect up to 12% of participants to drop out or otherwise become non-evaluable by 6 months, leaving 22 evaluable subjects per arm for the primary endpoint evaluation. We expect to randomize an average of 2-4 participants per month for each of the two participating CPN sites (Puerto Rico and Honduras), for an overall average accrual rate of 5-6 participants per month.

Amendment 6 Update: Because of delays related to regulatory and customs approvals, activation at Honduras was delayed by 15 months, which resulted in slower than expected overall accrual. Recently, the Honduras site discovered a higher than expected incidence of *Helicobacter pylori* infection, an exclusion criterion. In order to continue their expected recruitment pace, they expanded their outreach to more rural areas where *H. pylori* infection is somewhat less prevalent. They have also begun contacting participants who were screen failures in one previous study and who have completed another previous study as a group of known potential participants with high rates of study compliance. They are also reviewing lists of *H. pylori*-treated participants for evidence of gastric metaplasia and possible eligibility. The current anticipated completion date (last participant contact for the primary endpoint) is the 4th quarter of 2020.

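### The primary test ignores baseline IL-1β as a covariate and both allocation factors, and leaves the switch to Wilcoxon undefined; one pre-specified ANCOVA would usually have more power at almost no cost

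*Combined protocol and SAP*

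**What the plan says.** Section 13.4 defines the endpoint as absolute change in gastric mucosal IL-1β from baseline to 6 months. It powers the trial for a two-sample t-test with 22 evaluable participants per arm at one-sided 0.05, "assuming the same standard deviation of 7.5 pg/mg protein in each arm". The same section introduces that figure with the expected baseline mean of 14 pg/mg protein, "with a standard deviation of about 7.5 pg/mg of protein". It then provides for a change of test: "If the data are not normally distributed, we will use the Wilcoxon Rank-Sum test for the primary endpoint analysis".

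Section 13.2 allocates by the Pocock-Simon method: "For this study we will use the following stratification factors (collected at baseline, prior to randomization): enrolling site (Honduras or Puerto Rico"), the second factor being histologic diagnosis (MAG, GIM or both). Section 13.6 says that randomized participants with IL-1β at both times "will be evaluable for the primary endpoint of this study using the modified intent-to-treat principle", so every analysed participant has a baseline value. Section 13.8 adds that for the primary endpoint "the 95% confidence intervals will also be provided". Sections 13.5, 13.6 and 13.8 name no covariate, model or estimator for the primary comparison.

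**The concern.** Three things are left out.

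- **Baseline as a covariate.** Subtracting baseline fixes its slope at 1. If the correlation between visits is moderate, the best slope is smaller and the change score carries avoidable noise.
- **Site and histology.** They balance the allocation but are dropped from the analysis.
- **The rule for switching tests.** No normality test, threshold, timing or data set to be checked is given. The switch also replaces a difference in mean change by a rank comparison, and no confidence interval is defined for that case.

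A smaller point concerns the interval. A two-sided 95% interval corresponds to a one-sided 0.025 test, not to the planned one-sided 0.05 test.

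Only 44 evaluable participants are planned, so precision is scarce, and all the covariates are already collected.

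**Working it through.** **Inputs from Section 13.4.** Difference 7.0 − 0.5 = 6.5 pg/mg protein; SD 7.5; 22 per arm; one-sided 0.05. The correlation r is not in the documents; it is an assumption and is shown as a range. Equal SDs at both visits are assumed.

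**The plan's own figure.** Standard error = 7.5 × √(2/22) = 2.261. Noncentrality = 6.5 / 2.261 = 2.874. The noncentral t with 42 df gives 88.2% at one-sided 0.05, so the stated 88% reproduces. At one-sided 0.025 it gives 80.2%.

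**ANCOVA by formula.** With equal SDs, the variance of the ANCOVA estimate is (1 + r)/2 times that of the change-score estimate. If 7.5 is the SD of change, the residual SD is 7.5 × √((1 + r)/2). At r = 0.5 this is 6.50; the standard error is 6.50 × √(2/22) = 1.96, the noncentrality 6.5 / 1.96 = 3.32, and power with 38 df (baseline, site and two histology terms) is 94.7%. The formula assumes perfect covariate balance.

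**Simulation with realistic imbalance.** 20,000 trials per case. Fifty participants were allocated by Pocock-Simon, with 25 per site, an assumed 15/60/25% MAG/GIM/both split and an assumed biased coin of 0.8. Six of 50 were lost at random, following Section 13.3: "We further expect up to 12% of participants to drop out or otherwise become non-evaluable by 6 months". Data were normal, the SD of change was 7.5, and site and histology were uninformative. Simulation error is 0.1 to 0.2 points.

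| r | Implied SD of level | t-test, simulated | ANCOVA, baseline only, simulated | ANCOVA, all covariates, simulated | ANCOVA, all covariates, formula |
|---|---|---|---|---|---|
| 0.3 | 6.3 | 88.0% | 96.5% | 96.2% | 96.8% |
| 0.5 | 7.5 | 87.8% | 94.2% | 93.7% | 94.7% |
| 0.7 | 9.7 | 87.9% | 91.4% | 90.7% | 92.2% |
| 0.9 | 16.8 | 88.4% | 89.1% | 88.1% | 89.5% |

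Null size, simulated at r = 0.3, 0.5 and 0.9, was 4.8 to 5.2% for both the t-test and the full ANCOVA.

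**The other reading of 7.5.** Section 13.4 gives 7.5 for a level and then uses it for change. SD of change = 7.5 × √(2(1 − r)) equals 7.5 only at r = 0.5. If 7.5 is the SD of a level, the ANCOVA residual SD is 7.5 × √(1 − r²). Formula power, t-test against ANCOVA on baseline, is then 63.9% vs 88.1% (r = 0), 77.2% vs 90.6% (r = 0.3), 88.2% vs 94.7% (r = 0.5) and 97.8% vs 99.0% (r = 0.7).

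**The undefined switch.** In simulation with normal and lognormal levels, a fixed Shapiro-Wilk rule kept one-sided error at 5.0 to 5.3%. If the smaller of the two p-values could be taken, it was 5.7 to 6.7%. Nothing in the documents suggests that this is intended, but nothing excludes it.

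**Test and interval.** Under the planned alternative the t-test succeeds in 88.2% of trials and the 95% interval excludes zero in favour of Meriva in 80.2%. They disagree in 88.2 − 80.2 = 8.0% of trials.

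**Omitting the allocation factors (hypothetical).** If site and histology together explained 10% or 20% of the variance in change, the size of the unadjusted test would be about 4.3% or 3.7%, against 4.9% or 4.7% adjusted. The documents do not link either factor to IL-1β.

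**The case against.** The plan is valid as written, its power figure is right, and it exceeds 80% power under its own assumptions. On that view this is an efficiency preference in a phase 2 trial. That is true and limits the weight of the point.

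The size of the gain is also uncertain. It rests on an unknown r and vanishes near r = 0.9. Holding the SD of change at 7.5 implies level SDs that match Section 13.4 only at r = 0.5. This stands, but the alternative reading makes the gain larger at low r, so the range above does not overstate it.

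The sharpest objection is that the power table assumes normal data, whereas the plan would use Wilcoxon for non-normal data. With lognormal levels and an additive shift (6,000 runs, baseline-only ANCOVA), ANCOVA had 93.5% power and Wilcoxon 92.7% at r = 0.5, and 98.2% and 98.7% at r = 0.7. In that setting there is little or no gain. At r = 0.3 ANCOVA kept a lead (88.8% against 81.6% for a Shapiro-Wilk switch). With a multiplicative effect it led at every r tried; at r = 0.5 it had 99.7% against 93.9% for Wilcoxon.

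Finally, site and histology have no demonstrated value. If uninformative, they cost 0.3 to 1.0 point compared with baseline alone in the table, and up to about 2 points without balanced allocation. The case for them is that the analysis should reflect the allocation; the gain itself comes from baseline. The interval mismatch is a reporting matter that ANCOVA does not remove.

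**Conclusion.** The concern holds as a recommended improvement. The planned test is valid and correctly powered, but it makes limited use of a baseline value that every evaluable participant must have, and it leaves the primary test open.

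At r = 0.5, the only correlation consistent with both uses of 7.5, power rises by about 6 points in simulation (87.8% to 93.7%). Over r = 0.3 to 0.9, with the SD of change at 7.5, the gain runs from about 8 points to none. These figures assume normal data, equal SDs at both visits and uninformative site and histology. With skewed levels the advantage over Wilcoxon can disappear. The missing switch criterion and the interval level are secondary points that the same edit can settle.

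**What to change.** In Section 13.4, name one raw-scale primary model before unblinding: ANCOVA of 6-month IL-1β on arm, baseline IL-1β, enrolling site and baseline histology. Using change as the response gives the same arm coefficient.

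- **Histology value.** Use the local diagnosis that drove allocation, since under Section 10.2.3 "Central pathology review will be performed at one time, when the study is completed".
- **Sparse levels.** Fix a blinded merging rule. For example, a level with fewer than 5 evaluable participants, pooled over arms, is merged with the both category; if that category is the sparse one, it is merged with GIM. In a 15,000-run simulation at r = 0.5 this rule applied in 19.6% of trials and left power unchanged (93.9% with it, 93.8% without).
- **Test and interval.** Test the arm coefficient one-sided at 0.05. Report the 95% interval promised in Section 13.8, state that it corresponds to one-sided 0.025, and add the 90% interval that matches the test.
- **Sensitivity analyses.** Keep the unadjusted t-test, and the Wilcoxon test with a Hodges-Lehmann estimate and interval. Neither replaces the primary analysis on the basis of the data.

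The cost is small: no new data, visits or participants. Under Section 14.3 the change needs a DCP-approved amendment with CIRB/REB approval before it is implemented. The statistical price is the small loss noted above if site and histology prove uninformative.
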